2.3.5.2 Secondary efficacy outcomes

For binary efficacy outcomes (dichotomized mRS at day 90, reperfusion outcome in final angiogram, reperfusion outcome after the first pass, occurrence of emboli to a new territory, technical success rate and percentage of subjects with acceptable revascularization quality), between-group comparisons will be performed by using a Chi-squared test or Fisher's exact test when applicable. The binary secondary efficacy outcomes also will be analyzed by logistic regression analysis to provide an odds ratio and its 95% CI, if applicable. The adjustment factors are the same as those in the primary outcome analysis.

For continuous efficacy outcomes (infarction volume, the change in NIHSS score at 24 hours post treatment from baseline and change in NIHSS score at 7 days post treatment or discharge from baseline), between-group comparisons will be done using a linear model adjusted for the prognostic factors considered in the primary outcome analysis, as appropriate; the adjusted mean difference will be derived from a linear model as treatment effect sizes. In case of obvious deviation from normality of the model residuals (except if a logarithmic transformation or other common transformation could be applied), a non-parametric analysis with the Mann-Whitney U test will be used and standardized differences will be calculated. Rank-transformed data will be provided as treatment effect size.

For count variable (number of thrombectomy attempts), it will be analyzed by using a negative binomial model ^[3] with the count data as dependent variable and treatment group as fixed-effect factors adjusted for the prognostic factors considered in the primary outcome analysis, as appropriate. The model estimated event rates and its 95%

confidence intervals will be provided by treatment groups. The treatment comparison will be performed through the estimated ratio of risk rates.

For time-to-event variable (time from groin puncture to successful reperfusion), it will be analyzed using the Cox's proportional hazards model with a fixed treatment group factor and adjusted for the prognostic factors considered in the primary outcome analysis, as appropriate. The estimated hazard ratio and the corresponding two-sided 95% CI will be provided. The Kaplan-Meier curves by treatment groups will be presented.

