1.4 Estimation of Sample Size

In a meta-analysis ^[1] comparing BGC with conventional guide catheter, the use of balloon guide catheter improved the proportion of functional outcome by 10.8%. In this study, based on a more conservative estimate, we assume the usage of BGC would improve the function outcome by 8%. Based on the distribution of the mRS in the control group of the trial, which we derived from the intervention group of the MR CLEAN trial : mRS0: 3%; mRS 1: 9%; mRS 2: 21%; mRS 3: 18%; mRS 4: 22%; mRS 5: 6% and mRS 6:21%. We assumed a favorable treatment effect with a common odds ratio (cOR) of 1.43, corresponding to an 8% absolute increase in the rate of mRS scores of 0-2. In a simulation with 5000 runs we computed the proportion of positive trials, for a given sample size. A sample size of 1074 subjects is estimated to be able to demonstrate this treatment effect with 87% power and 5% type-1 error. This sample size also allows for 5% dropout rate and 5% crossover rate.

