1.5 Randomization and Treatment allocation

Subjects will be randomized via an internet-based randomization system in a 1:1 manner to treatment with BGCs (Intervention group) or not (Control group), stratified by site, preferred initial thrombectomy strategy (stent retriever vs. aspiration vs. stent retriever + aspiration), and onset to randomization time (<6 hours vs. \geq 6 hours). The randomization sequence will use a minimization algorithm to ensure balance in these key prognostic factors. Randomization is allowed when large vessel occlusion has been established.

Subjects will be treated with thrombectomy based on the results of randomization:

- Intervention group: Subjects treated with BGCs combined with conventional thrombectomy.
- **Control group**: Subjects treated with conventional guide catheter combined with conventional thrombectomy.

Any National Medical Products Administration (NMPA) approved devices (including thrombectomy stent, aspiration catheter, or combined use of both) are allowed in this study.

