2.3.5.1 Primary efficacy outcome

The distribution of the mRS score at day 90 will be reported for each treatment group. The primary efficacy outcome analysis will be conducted by using ordinal logistic regression analysis adjusted for prognostic factors, including center as a random effect, preferred initial thrombectomy strategy (stent retriever vs. aspiration vs. stent retriever + aspiration), onset to randomization time (continuous), mRS before stroke (categorical), age (above vs. below median), and baseline NIHSS (above vs. below median) as fixed covariates. Adjusted and unadjusted common proportional odds ratio (cOR) for 1-point improvement in the mRS score will be derived from this model as treatment effect size (intervention group vs. control group) with their corresponding 95% confidence interval (CI). In case of deviations in proportional odds assumption, the mRS score at day 90 will be compared between groups by using the Mann-Whitney U test, and Wilcoxon-Mann-Whitney generalized OR will be calculated as effect size ^[2].

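### Binary secondary outcomes take their test from an unadjusted chi-squared or Fisher's exact test but their odds ratio and 95% CI from an adjusted logistic model, so p-value and CI can disagree

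*SAP*

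**What the plan says.** SAP 2.3.5.2 covers the dichotomised mRS, final and first-pass reperfusion, emboli to a new territory, technical success and the 45-minute revascularisation outcome. For these, "between-group comparisons will be performed by using a Chi-squared test or Fisher's exact test when applicable". The SAP then adds: "The binary secondary efficacy outcomes also will be analyzed by logistic regression analysis to provide an odds ratio and its 95% CI, if applicable". On that model it says: "The adjustment factors are the same as those in the primary outcome analysis". Under SAP 2.3.5.1 those factors are centre as a random effect, preferred initial strategy, onset-to-randomisation time, and "mRS before stroke (categorical), age (above vs. below median), and baseline NIHSS (above vs. below median) as fixed covariates".

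The same section treats other outcome types differently. For continuous outcomes, "between-group comparisons will be done using a linear model adjusted for the prognostic factors considered in the primary outcome analysis, as appropriate", with a rank-test fallback for non-normal residuals. The count outcome uses an adjusted negative binomial model, and the time-to-event outcome an adjusted Cox model.

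Allocation is minimised on site, preferred strategy and onset-to-randomisation time (SAP 1.5: "The randomization sequence will use a minimization algorithm to ensure balance in these key prognostic factors"). Protocol 7.2 names a model only for the primary outcome and leaves the rest to the SAP.

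**The concern.** The p-value from the stated comparison and the interval printed beside it come from different analyses. One ignores all covariates, including the minimisation factors; the other uses them. A result can then show p < 0.05 with a CI that includes 1, or the reverse. The SAP does not say how such a result is to be read, or whether a model p-value will also appear.

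Counting from SAP 2.1.2.2, this touches 15 binary endpoints: five mRS cuts, three final eTICI levels, three first-pass levels, two 45-minute levels, emboli and technical success. Each is repeated in the per-protocol set (SAP 2.3.5).

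Where the covariates predict the outcome, the unadjusted test also has less power than the model the SAP already intends to fit.

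**Working it through.** **Inputs from the documents.** The control mRS distribution in SAP 1.4 is "mRS0: 3%; mRS 1: 9%; mRS 2: 21%; mRS 3: 18%; mRS 4: 22%; mRS 5: 6% and mRS 6:21" (per cent), so mRS 0-2 = 3 + 9 + 21 = 33%. The common odds ratio is 1.43. The protocol synopsis gives N = 920 for 87% power at two-sided 0.05, and 1074 (537 per arm) after 5% dropout and 5% crossover.

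**The plan's own figures reproduce.**
- Effect: odds 0.33/0.67 × 1.43 = 0.704, so mRS 0-2 becomes 0.704/1.704 = 41.3%, a rise of 8.3 points (stated 8%).
- Power (Whitehead): V = (N/12)(1 − Σp̄³) = (920/12)(1 − 0.0348) = 74.0. Power = Φ(ln 1.43 × √74.0 − 1.96) = Φ(0.358 × 8.60 − 1.96) = Φ(1.117) = 86.8% (stated 87%).
- Inflation: 920/0.95/0.95² = 1073.04, hence 1074.

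**Chi-squared power for mRS 0-2 by formula**, n = 537 per arm: Φ{(Δ√n − 1.96√(2p̄q̄))/√(p₁q₁ + p₂q₂)}. For 33% vs 41% this is Φ{(0.08 × 23.17 − 1.96 × 0.683)/0.680} = Φ(0.758) = 77.6%. For 33% vs 41.3% it is 80.7%.

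**Simulation on the same data.** N = 1074, 33% vs 41%, 3000 trials per row, two-sided 0.05. It compares Pearson chi-squared with the Wald test from a logistic model containing median-split NIHSS, median-split age, pre-stroke mRS, onset time and strategy. The covariate odds ratios are assumptions, as is 20% of patients at the higher pre-stroke mRS. The log-odds SD is √{(ln OR_NIHSS/2)² + (ln OR_age/2)² + 0.16(ln OR_mRS)²}.

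| OR for NIHSS / age / pre-stroke mRS | Log-odds SD | Chi-squared | Adjusted | Only chi-squared significant | Only adjusted significant | Disagree |
|---|---|---|---|---|---|---|
| 1 / 1 / 1 | 0 | 78.1% | 78.3% | 1.0% | 1.2% | 2.1% |
| 1.5 / 1.5 / 1.3 | 0.3 | 76.9% | 78.2% | 1.2% | 2.5% | 3.7% |
| 2.5 / 2 / 1.5 | 0.6 | 77.8% | 80.2% | 2.2% | 4.7% | 6.9% |
| 4 / 3 / 2 | 0.93 | 79.3% | 85.3% | 1.7% | 7.7% | 9.4% |
| 2.5 / 2 / 1.5, no treatment effect | 0.6 | 4.9% | 4.7% | 1.4% | 1.2% | 2.6% |

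For the four rows with a treatment effect, the power gain is 0.2 / 1.3 / 2.4 / 6.0 points. A repeat run with the same odds ratios gave gains of 0.1 / 1.0 / 3.3 / 6.4 points, disagreement of 2.0% / 4.0% / 7.0% / 10.3%, and type I error of 4.5% (chi-squared) and 5.0% (adjusted). A separate run at n = 1020 (1074 × 0.95) with 33% vs 41.3% gave gains of about 0 to 6 points and disagreement of about 1% to 10%.

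**Limits.** Covariates were allocated by simple randomisation, not minimisation. In the tabulated run, centre variation was generated but not fitted as a random effect. Only mRS 0-2 was simulated. The SAP's final level of 0.0482, if applied to secondary outcomes, would add a slight further mismatch with a 95% CI; that is not counted here.

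**The case against.** The strongest reply is that each method has a stated task: chi-squared or Fisher compares, and the logistic model estimates. Both are specified in advance and valid, and these are secondary outcomes in a trial whose primary analysis is already adjusted. That reply largely stands, and it limits what can be claimed.

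- A reader might infer that no lead test is specified. The text does not support that: the comparison is assigned to chi-squared or Fisher. What it leaves open is whether a model p-value is also reported, and how a conflict with the CI is read.
- A reader might infer a false-positive problem from ignoring the minimisation factors. The null simulation shows none. Leaving such factors out of the test tends to make it slightly conservative, not invalid.
- A reader might infer a larger power loss. A single continuous prognostic score with log-odds SD 1.3 gives an 11-point gain (77% to 88%) and 14% disagreement. The SAP adjusts for age and NIHSS only as median splits. For two equal splits to reach that SD, each needs ln OR = 1.3 × √2 = 1.84, an odds ratio of about 6.3. Even SD 1.0 needs about 4.1. Pre-stroke mRS adds little, because eligibility limits it to 0-1.
- A reader might extend the power claim to every binary outcome. Nothing in the documents shows that age, NIHSS or pre-stroke mRS predict reperfusion, technical success, emboli or the 45-minute outcome.
- A reader might think the change is free. The adjusted odds ratio is conditional and need not equal the crude one. A random-centre model over 40-60 sites may fail for rare events, which may be why the SAP makes the logistic model conditional.

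The mismatch itself survives. Even when NIHSS, age and pre-stroke mRS carry no information, the two analyses disagree in about 2% of the simulated trials above, and no other section resolves it.

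**Conclusion.** The point holds as a matter of consistency, with a modest efficiency gain for dichotomised mRS. The documents establish the unadjusted test, the adjusted interval and the contrast with the other secondary outcomes. The sizes are less certain: the ranges of 0 to 6 points of power and 1% to 10% disagreement depend on assumed covariate strengths and were simulated for mRS 0-2 alone. Disagreement runs in both directions. Neither the validity of the tests nor the primary analysis is in question. The change is worth making before database lock because it is cheap and removes a conflict that would be awkward to settle once results are known.

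**What to change.** Amend SAP 2.3.5.2 as follows:
- For each binary secondary outcome, take the p-value, odds ratio and 95% CI from the adjusted logistic model with the primary-analysis factors.
- Show raw counts and percentages by arm.
- Keep chi-squared only as a labelled sensitivity analysis.
- Use Fisher's exact test under a sparse-data or non-convergence rule that is written out and fixed before database lock, in place of the present open conditions. Where the rule applies, take the interval from the same unadjusted analysis, so that p-value and CI still match.

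The cost is a few sentences. The model and its covariates are already planned, so no new data are needed. The price is a conditional odds ratio, which the raw percentages put in context, and possible model failure for rare events, which the fallback covers.

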2.3.5.3 Subgroup analyses

For the primary outcome, pre-specified subgroup analyses will be performed by examining the interaction between specific baseline characteristics and treatment. Subgroups are defined as follows:

- age (above vs. below median)
- onset time to randomization (<6 vs. \geq 6 h)
- NIHSS at baseline (above vs. below median)
- occlusion location (internal carotid artery vs. middle cerebral artery)
- presumed etiological AIS subtype (intracranial atherosclerosis vs. extracranial lesion vs. cardioembolism vs. other/undetermined)
- preferred treatment strategy (stent retriever vs. aspiration vs. stent retriever + aspiration)
- Tandem lesion (Yes vs. No)
- Intravenous thrombolysis (Yes vs. No)

The analysis for each subgroup will be performed by adding the subgroup variable as well as its interaction with the intervention as fixed effects to the main logistic regression model. Within each subgroup, summary measures will include raw counts and percentages by treatment arm, as well as the OR for treatment effect with a 95% CI. The output results will be displayed on a forest plot, including the p-values for heterogeneity corresponding to the interaction term between intervention and each subgroup variable.

2.3.6 Safety analysis

In this study, the safety analysis will be mainly based on statistical description. All of the safety data analyses will be performed in both ITT and PPS.

2.3.6.1 Analysis of AEs

The number and percentage of subjects who had at least one serious adverse event, classification of serious adverse event, adverse events of intracranial hemorrhage and symptomatic intracranial hemorrhage or asymptomatic intracranial hemorrhage at 7 days post treatment or discharge.

- All SAEs will be summarized by SOC and PT;
- Any peri-procedural complications will be summarized by SOC and PT.

In order to signal potential safety problems, comparisons of the frequency of SAEs and peri-procedural complications between treatment groups will be performed by using a Chi-squared test or Fisher's exact test when appropriate.

The data listings will be provided for All SAEs, any procedural complications and deaths at 90 days post treatment.

2.3.6.2 Analysis of vital signs

Summaries of vital signs parameters will be presented by treatment groups, using summary statistics for observed values for each parameter.

2.3.6.3 Clinical laboratory data analysis

For continuous laboratory parameters, the summary statistics will be provided by treatment groups for observed values for each parameter.

If a lab test result is recorded as "<10", then it will be summarized as a value of "5", if applicable; and likewise, ">10" will be summarized as "10".

2.3.7 Cost outcomes analysis

For the EQ-5D dimensions, between-group comparisons will be done using a linear model adjusted for the prognostic factors considered in the randomization, as appropriate; the adjusted mean difference will be derived from a linear model as treatment effect sizes.

For other cost outcomes, they will need time to acquire and analyze, and hence will be presented in a secondary analysis and publication, which is out of the analysis scope of the SAP.

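### The 90-day EQ-5D comparison is adjusted only for the randomization factors, while every other modelled outcome also adjusts for pre-stroke mRS, age and baseline NIHSS; aligning it is a free, minor gain in precision

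*SAP*

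**What the plan says.** SAP 2.3.7 (cost outcomes) sets the EQ-5D analysis as a between-group comparison "using a linear model adjusted for the prognostic factors considered in the randomization", with the rider that this is done as appropriate. It does not list the factors.

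SAP 1.5 identifies them. Randomization is "stratified by site, preferred initial thrombectomy strategy (stent retriever vs. aspiration vs. stent retriever + aspiration), and onset to randomization time" (below 6 hours against 6 hours or more), and "The randomization sequence will use a minimization algorithm to ensure balance in these key prognostic factors". Pre-stroke mRS, age and baseline NIHSS are not among them.

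SAP 2.3.5.1 gives the primary mRS model a longer list: center as a random effect, preferred strategy, onset-to-randomization time as a continuous variable, and then "mRS before stroke (categorical), age (above vs. below median), and baseline NIHSS (above vs. below median) as fixed covariates".

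SAP 2.3.5.2 carries that longer list to all modelled secondary outcomes. For the logistic models, "The adjustment factors are the same as those in the primary outcome analysis". For the continuous outcomes, "between-group comparisons will be done using a linear model adjusted for the prognostic factors considered in the primary outcome analysis". The negative binomial model for thrombectomy attempts and the Cox model for time to reperfusion refer to the same list.

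The visit schedules (Protocol 6.2.1 and SAP 1.6, Table 1) place EQ-5D at day 90 only.

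**The concern.** EQ-5D is the one modelled outcome with the shorter adjustment set. It is collected at the same 90-day visit as the primary mRS, for which the SAP itself treats pre-stroke mRS, age and baseline NIHSS as prognostic. The linear-model sentences in SAP 2.3.5.2 and 2.3.7 are close to identical except for which covariate list they cite, and nothing explains the difference.

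The stake is the precision of the EQ-5D difference. In a linear model, leaving out baseline variables that predict the outcome leaves their share of the variance in the residual, which widens the confidence interval. EQ-5D is also the only cost outcome that this SAP analyses; the others are deferred to a later publication.

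**Working it through.** **1. Covariate lists side by side**

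| Covariate | EQ-5D (SAP 2.3.7, via 1.5) | Primary and other modelled outcomes (SAP 2.3.5.1, 2.3.5.2) |
|---|---|---|
| Site / center | yes | yes (random effect) |
| Preferred initial strategy | yes | yes |
| Onset to randomization | yes (<6 h vs ≥6 h in the randomization) | yes (continuous) |
| Pre-stroke mRS | no | yes (categorical) |
| Age | no | yes (median split) |
| Baseline NIHSS | no | yes (median split) |

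**2. The plan's own figures.** Neither document states a standard deviation, effect size or power for EQ-5D. The one stated power figure concerns the primary mRS shift: 87% with 920 patients and a common odds ratio of 1.43. It reproduces with the proportional-odds formula, power = Φ(|ln 1.43| × √[N/12 × (1 − Σp̄³)] − 1.96), where p̄ is the mean of the two arms' mRS probabilities. With N = 920 this gives 86.8%. The sample size therefore rests on mRS alone, and nothing below alters it.

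**3. Precision formula.** Let R² be the share of EQ-5D variance that the three added covariates explain beyond the randomization factors. Then:

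- standard error with the covariates ÷ standard error without = √(1 − R²)
- equivalent extra sample = 1/(1 − R²) − 1
- power under the planned model for an effect with 80% power under the fuller model = Φ[(1.960 + 0.842) × √(1 − R²) − 1.960]

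None of these depends on the number of patients.

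**4. Range for R² (assumption).** R² is not in the documents. Two features of the SAP's coding argue for a modest range. Eligibility restricts pre-stroke mRS to 0-1 (Protocol 4.1), so it has two levels among eligible patients. Age and NIHSS enter as median splits; for a roughly normal predictor with a linear effect, a median split keeps about 2/π = 64% of the variance explained. If continuous versions explained 10-25%, the split versions would explain about 0.64 × 10% = 6% to 0.64 × 25% = 16%. I use 5-15%.

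| R² | SE ratio | SE reduction | Equivalent extra sample | Power under planned model |
|---|---|---|---|---|
| 0.05 | √0.95 = 0.975 | 2.5% | 1/0.95 − 1 = 5.3% | 78.0% |
| 0.10 | √0.90 = 0.949 | 5.1% | 1/0.90 − 1 = 11.1% | 75.7% |
| 0.15 | √0.85 = 0.922 | 7.8% | 1/0.85 − 1 = 17.6% | 73.3% |

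**5. Chance imbalance is the same loss, not a second one.** With n = 537 per arm, the standardized difference of a covariate outside the minimization has SD √(2/537) = 0.061, with a 95% limit of 1.96 × 0.061 = 0.12. At that limit the estimate moves by √R² × 0.12, which is 0.027 outcome SD for R² = 0.05 and 0.046 for R² = 0.15. The variance of this shift, in outcome-SD units, is R² × 2/n. That is exactly the gap between 2/n without the covariates and (1 − R²) × 2/n with them. The wider interval already contains it.

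**The case against.** The strongest reply is that the analysis is sound as written. Adjusting for the factors used in randomization is a legitimate, pre-specified choice, and omitting other baseline variables does not bias a randomized comparison. A reader might infer from the mismatch that the EQ-5D estimate is biased or invalid. The documents do not support that; only efficiency is at issue.

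Other parts of the reply also stand:

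- **Importance.** EQ-5D is a cost outcome, separate from the primary, secondary and safety outcomes (SAP 1.3). Neither the sample size (SAP 1.4) nor the interim rules (SAP 4) depend on it.
- **Other predictors.** A reader might suppose that the three omitted covariates are the only recorded patient-level predictors. They are not: GCS, medical history, glucose and baseline imaging are collected too (Protocol 6.2.2.1), and onset time stays in the EQ-5D model. The three are the additional ones that the primary analysis already uses.
- **Size.** A gain of 5-13% in the standard error would need R² of 10-25% from the covariates as coded, which the median splits and the mRS restriction make doubtful. SAP 2.3.7 also analyses EQ-5D by dimension, so one R² need not hold throughout.
- **Uniformity.** Full adjustment is not the rule everywhere. Binary outcomes are also compared by chi-squared or Fisher tests, and safety comparisons are unadjusted (SAP 2.3.5.2, 2.3.6.1). The mismatch is among modelled outcomes only.

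One argument does not stand. The rider allowing the covariates to be used as appropriate names none of the missing ones, and it also appears in SAP 2.3.5.2, so it does not explain the difference.

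A separate question remains. SAP Table 3 gives no EQ-5D value for patients who die, although SAP 1.4 assumes 21% control mortality. If only survivors are compared, which the SAP does not say, the protection from randomization no longer fully applies under either covariate set. Aligning the covariates would not settle that.

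**Conclusion.** The inconsistency is real and unexplained: EQ-5D has a shorter covariate set than every other modelled outcome. The planned comparison of the randomized groups is valid and unbiased over repeated randomizations; what it gives up is precision. On the assumption that the added covariates, as coded in the SAP, explain a further 5-15% of variance, the standard error would fall by about 3-8%, equal to about 5-18% more patients for this outcome. That range is illustrative, because no R² is given and the gain may vary by dimension. The direction, a gain whenever these covariates explain a meaningful share of the variance, follows from the linear model. This is a minor point and a free improvement. It cannot change the primary conclusion.

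**What to change.** Before database lock, change the adjustment clause in SAP 2.3.7 so that it refers to the primary outcome analysis rather than to the randomization, matching SAP 2.3.5.2: "linear model adjusted for the prognostic factors considered in the primary outcome analysis". The EQ-5D model would then use center (random effect), preferred strategy, onset time, pre-stroke mRS, age and baseline NIHSS. This also settles how center and onset time enter the EQ-5D model, which SAP 2.3.7 leaves unsaid.

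The cost is one phrase in the SAP. All the covariates are collected at baseline and already used in the primary model. No change to data collection, sample size or the primary analysis follows.
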